## 6.0 Study Interventions\*

**Description:** *Describe the study intervention and/or experimental manipulation that is being evaluated.* The Study design is to distribute willow pumps directly before birth of child for subjects that choose to enroll in the study, pumps will be provided prior to

individual going on leave, this allows individuals to have devices at home and practice with them before returning to work.

Research procedures will include subjects to complete the consent and intake survey at initiation of pumping, completing monthly surveys through pumping and then a endpoint survey to collect final experiential data.

Describe:

Individual will be provided Willow Pumps prior to delivery and leave to allow for practice.

Willows are single user devices per FDA regulations

The institution will provide educational materials for users and access to Willow experts for support

Attachments included: consent form, intake, monthly and endpoint surveys.

Data collected during survey

INTAKE SURVEY – expectation and goals for lactation experience, demographics and knowledge of lactation from previous experiences.

MONTHLY SURVEY – changes to lactation practices, current volume, frequency and satisfaction.

OUTTAKE SURVEY – final experience input, expectations vs reality, total length of time pumping and providing milk

No current plans for long-term follow-up

Not a Humanitarian Use Device (HUD)

**6.1 Behavioral Intervention:** *If this study involves a behavioral intervention, describe the intervention in detail. Be sure to address whether the intervention is experimental or considered to be an accepted standard.*

- **Deception:** *If the study includes any aspect of deception, explain the deceptive aspects as well as the scientific rationale for the deception.*

N/A

**6.2 Drugs, Biologics, or Devices:** *If this study involves the administration or dispensation of a drug or biologic, or the use of a medical device (including mobile medical apps), within FDA approved labeling or outside of FDA regulation, complete the table below.*

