#### Inclusion Criteria

Participant eligibility will be based on employment or enrollment in a CMKC residency or fellowship program. Participant eligibility will be obtained via self-enrollment, individuals will self-identify and notify investigators when they are going to start pumping. Some parents are proactive and plan out ahead of time their lactation needs, some pivot from original plan after returning to work and request support after initiation, intervention will accommodate both and surveys will begin at pumping initiation.

The specific population of study will be individuals of birthing age that give birth while in a CMKC residency or fellowship program and have determined that they plan to provide human milk and pump at work post-delivery.

**7.2 Equitable Selection:** *Inclusion/exclusion criteria should be both fair and appropriate to the research question. If the study involves inclusion/exclusion criteria based on demographic characteristics such as sex, race/ethnicity, language, provide rationale for the criteria. For example, if excluding non-English speaking participants, provide rationale for why it is not possible to include non-English speaking participants.*

**7.3 Vulnerable Populations:** *Check any vulnerable populations that are being targeted for enrollment into the study: (Members of the following populations may not be included as participants in the research unless selected here.)*

 Children/Minors (under 7 years of age)	 Non-Viable Neonates (infants less than 30 days old)
 Children/Minors (7-17 years of age)	 Wards of the State
 Neonates (infants less than 30 days old)	 Fetuses
 Neonates of Uncertain Viability (infants less than 30 days old)	 Pregnant Women

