## SHORT TITLE: Lactation at Work

 Adults with impaired decision-making capacity	 CM Employees
	 CM Students/Residents/ Fellows
	 Economically or Educationally Disadvantaged Persons
	 Prisoners

- *For each population selected above, describe the additional safeguards designed to protect their rights and welfare. To ensure that sufficient detail is provided, see the “Tips and Tools for Vulnerable Populations” below for more detailed information on the appropriate protections for each specific population.*
- *If the research involves enrolling CM employees or students, indicate how the potential for employees/students to feel coerced or unduly influenced to participate will be minimized. For example, the risk of coercion may be minimized by ensuring that employees will not be recruited or enrolled by their direct supervisor.*

This protocol is specifically designed for individuals to use a device already in the market designed for lactation (post pregnancy). There could be circumstances where a user becomes pregnant while also providing milk for an existing child, which is also a norm in this population. The risk of coercion for residents and fellows will be minimized by ensuring that employees will not be recruited or enrolled by their direct supervisor.

We will collect the baby's Date of Birth making them a secondary participant. No other information about the baby will be collected. The DIB is collected in order to start the monthly lactation emails. Questions during the survey are targeting the mother's experiences with lactation. Mother's will be asked how old their child is in each monthly survey in order to verify the number month survey and month of pumping are lining up correctly.

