#### Written Informed Permission/Consent

Written informed permission of parent/LAR for pediatric participants

Study group(s) to which this method applies:

Written informed consent of adult participants

Study group(s) to which this method applies: All participants

SHORT TITLE: Lactation at Work

Informed consent will be obtained at the beginning of the survey process at device handoff, individuals will complete the consent form which will trigger the survey timing.

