**Waiver/Alteration of consent of adult participants**

Study group(s) to which this method applies: Primary participants, moms. The consent form will be provided electronically for them to indicate agreement and consent. All participants

Informed consent will be obtained at the beginning of the survey process at device handoff, individuals will complete the consent form which will trigger the survey timing.

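### Consent and the intake goal survey are timed two ways; read literally, Section 6.0 supplies the pump before consent and leaves recipients who never start pumping with no recorded goal

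*Protocol*

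**What the plan says.** **Device.** Section 6.0 of the Protocol plans to "distribute willow pumps directly before birth of child for subjects that choose to enroll in the study", and repeats: "Individual will be provided Willow Pumps prior to delivery and leave to allow for practice". Sections 5.1 and 6.2 also allow the manufacturer to ship the pump directly.

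**Consent and intake at the start of pumping.** Section 6.0 continues: "Research procedures will include subjects to complete the consent and intake survey at initiation of pumping". Section 7.1 recognises women who plan ahead and women who ask for support after they have begun, and says "intervention will accommodate both and surveys will begin at pumping initiation".

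**Consent at handoff.** Section 21.1, under written consent, says: "Informed consent will be obtained at the beginning of the survey process at device handoff". The same section, under waiver or alteration of adult consent, repeats this and adds that "individuals will complete the consent form which will trigger the survey timing". Section 5.1 gives the device at enrolment, in exchange for an agreement to complete the surveys. The Table of Events in Section 5.2 marks consent, delivery of the pump and lactation-goal expectations all in the intake column.

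**A further trigger.** Section 7.3 says of the baby's date of birth: "The DIB is collected in order to start the monthly lactation emails". It adds that mothers are asked the child's age in each monthly survey, to check that survey month and pumping month agree.

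**The concern.** The protocol does not fix the order of three events: consent, recording of the intended goal, and receipt of the pump. For a study of intended against actual pumping (Section 3.3), that order decides what the baseline goal means and who has one.

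Three things are at stake if the Section 6.0 sentence is followed.

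- The device would be supplied before consent. Under the data-sharing table in Section 5.1 it would also be logged with the recipient's email address before consent.
- The goal would be stated after the birth and with the pump already in hand, when it may have been adjusted to what looks feasible.
- A recipient who never starts pumping would never reach consent or intake. She would have no goal to be judged against, and no later analysis can supply one.

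Section 2.1 asks what access to the pump does and expects results better than national metrics. There is no control group in which the same omission would occur and cancel.

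**Working it through.** The protocol states no figure that depends on this timing, so there is nothing to reproduce. The check sets the sections side by side and then does simple arithmetic on the denominator.

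**Step 1: order of events in each place**

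| Protocol section | Pump received | Consent and goal recorded | What starts the surveys |
|---|---|---|---|
| 6.0 | before delivery and leave | at initiation of pumping | not stated |
| 7.1 | not stated | not stated | initiation of pumping |
| 21.1 (two places) | handoff | consent at handoff | consent form |
| 5.1 | at enrolment | survey agreement at enrolment | not stated |
| 5.2 Table of Events | intake column | intake column | not stated |
| 7.3 | not stated | not stated | date of birth (monthly emails) |

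For a woman who receives the pump before birth, handoff and initiation of pumping are different dates. Section 6.0 and Section 21.1 therefore cannot both be followed. For a woman who asks for a pump after she has begun pumping, the goal is stated after pumping began under either rule, so she needs separate identification whichever rule is kept.

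**Step 2: who is recorded if Section 6.0 is followed**

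- A recipient who starts pumping, even briefly, has consent and a goal recorded at initiation.
- A recipient who never starts has neither. She still fits the population in Section 7.1, which is defined by a plan to pump at work, and she has had access in the sense of Section 2.1.

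**Step 3: direction and possible size**

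Let p be the share of starters who meet their goal and s the share of recipients who never start. Counting never-starters as not meeting their goal:

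rate among all recipients = p × (1 − s)

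Inputs: p = 0.75, borrowed for illustration from the earlier programme's figure for users who met or exceeded their pumping goal (Section 3.3, 2025 literature update). The values of s are assumed, because the protocol gives none.

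- s = 0.04: 0.75 × 0.96 = 0.72
- s = 0.12: 0.75 × 0.88 = 0.66
- s = 0.20: 0.75 × 0.80 = 0.60

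With 25 recipients (the yearly enrolment goal in Section 8.1) these shares are 1, 3 and 5 women. If only starters have a goal on record, 75% is reported in every case, an excess of 3, 9 or 15 points. Since p × (1 − s) is never above p, the omission cannot lower the reported rate.

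**The case against.** The strongest reply is that one sentence in Section 6.0 is out of line and the rest of the protocol shows the intended order. Section 6.0 itself limits distribution to those who choose to enrol, Sections 5.1, 5.2 and 21.1 put device and consent together, and Section 24.2 gives the consent form at the beginning. Section 7.1 speaks of when surveys begin, not of consent. This is fair as a reading of intent, but the contrary instruction remains and site staff could follow it. Direct shipment also leaves no in-person handoff to which consent could be attached.

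It can also be said that the choice of denominator belongs in an analysis plan that is not shown here. That holds for the analysis rule. It does not hold for consent and goals that were never collected.

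A reader might infer more than the documents support:

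- *That never-starters vanish altogether.* They do not. Section 5.1 has the team log each device with an email address, so a list of recipients exists. What is missing is consent and a goal.
- *That all early failures are lost.* Women who start and soon stop are captured at initiation. Only never-starters are missed.
- *That the goal is always stated after using the device.* Initiation may coincide with first use. For women supplied before birth, what is certain is that the goal follows the birth and receipt of the pump. The monthly surveys also record later changes in goals.
- *That monthly results cannot be aligned, or that surveys will arrive before birth.* The child's age is asked every month, and Sections 7.3 and 21.1 can be read together: consent opens the sequence and the birth date starts the emails.
- *That the 56% in Section 3.3 is a goal-attainment rate.* It is 23 of all 41 users pumping beyond 7 months, while 31 of 41 intended 7 months or more.
- *That the 6 to 8 weeks of leave in Section 3.3 measures the gap from handoff to birth.* It is the length of parental leave that most boards allow.

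**Conclusion.** The point stands as a contradiction in the current text. Section 6.0, supported on survey timing by Section 7.1, cannot be reconciled with Section 21.1 or with Sections 5.1 and 5.2 for women supplied before birth, and Section 7.3 adds a third time origin for the monthly emails.

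Under the literal Section 6.0 order, never-starters have no consent and no goal, and reported goal attainment can only be pushed upward. This direction rests on counting a never-starter as not having met her goal, which follows from a population defined by its plan to pump. The size is unknown. The range of 72% to 60% against a reported 75% depends wholly on the assumed non-start rates and the borrowed 75%, and is not an estimate for this study. If staff follow Section 21.1 and collect the goal at the same time, the consent and missing-goal problems do not arise. The documents therefore do not show that the study will be biased, only that one of its own instructions would make it so.

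**What to change.** Reconcile Sections 5.2, 6.0, 7.1, 7.3 and 21.1 to one sequence before pumps are distributed:

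1. E-consent and the intake survey, including intended duration, are submitted before a pump is handed over or shipped. This is the order that Sections 5.2 and 21.1 already support.
2. Monthly surveys are scheduled and indexed from the baby's date of birth, with the child's age already asked each month as the check.
3. Goal attainment is reported among all consented recipients, with never-starters counted as not meeting their goal.
4. Women who enrol after pumping has begun complete the same intake before handover and are flagged, so that their goals can be shown separately.

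The cost is protocol wording, a change to the REDCap trigger, and some means of obtaining the birth date after a prenatal handoff, such as one short prompt. The attainment rate may look less favourable. Goals not recorded before handover cannot be recovered later.

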**NOTE, if the study is:**

- *Evaluating of the safety or effectiveness of a drug, biologic, or medical device,*
- *Using a drug, biologic, or medical device outside of current FDA approved labeling, or*
- *If your study requires an IND, IDE or HDE*

*Then this is not the protocol template that should be used. Refer to the [CM Clinical Trial Protocol Template](#) which is designed for these types of clinical investigations.*

Drug/Biologic/Device Name	Describe how the article is being used under current FDA approved labeling
Willow wearable breast pump	Willows are single user devices per FDA regulations
Mobile app	Not FDA approved; Mobile app is being used under current labeling. Per FDA's policy for Device Software Functions and Mobile Medical Applications. The Willow Mobile app qualifies as

SHORT TITLE: Lactation at Work

	NOT a Medical device per example 6: Software functions that are intended for individuals to log, record, track, evaluate, or make decisions or behavioral suggestions related to developing or maintaining general fitness, health or wellness.

- **Drug Handling:** *Describe plans to store, handle, and administer the drugs so that they will be used only on participants and by authorized investigators.*
  - *Reference the established, approved organizational SOP (e.g. Research Pharmacy SOP for the Control of Investigational Drugs) that will be followed. If deviating from approved SOPs, explain why the approved SOPs would not suffice for this study and the rationale for deviating.*
- **Device Handling:** *Describe plans to store, handle, and administer the device(s) used in this study so that they will be used only on participants and by authorized investigators.*
  - *Reference the established, approved organizational SOP (e.g. Research Policy 7.04 Investigational Devices - Control), that you will be following. If deviating from approved SOPs, explain why the approved SOPs would not suffice for this study and the rationale for deviating.*

Devices stored in GME or shipped directly to individuals from Willow. No special handling needed for devices, individuals responsible for cleaning and maintenance, devices covered under warranty for first year. (*Products are covered under manufacturer 1 year warranty. All Mom's are asked to contact Willow directly for warranty/troubleshooting and exchange/replacement requests) Please see our site for in depth warranty information <https://onewillow.com/pages/faq>. Our customer care team number to call is located here with days/times for live help and other avenues of communication to obtain live help. <https://onewillow.com/pages/contact>*)

## PARTICIPANT MANAGEMENT

### 7.0 Inclusion and Exclusion Criteria\*

**7.1 Eligibility Criteria:** *Describe the criteria that define who will be included or excluded in the final study sample. If the study design includes multiple groups, be sure to list the criteria for each group.*

#### Inclusion Criteria

Participant eligibility will be based on employment or enrollment in a CMKC residency or fellowship program. Participant eligibility will be obtained via self-enrollment, individuals will self-identify and notify investigators when they are going to start pumping. Some parents are proactive and plan out ahead of time their lactation needs, some pivot from original plan after returning to work and request support after initiation, intervention will accommodate both and surveys will begin at pumping initiation.

The specific population of study will be individuals of birthing age that give birth while in a CMKC residency or fellowship program and have determined that they plan to provide human milk and pump at work post-delivery.

**7.2 Equitable Selection:** *Inclusion/exclusion criteria should be both fair and appropriate to the research question. If the study involves inclusion/exclusion criteria based on demographic characteristics such as sex, race/ethnicity, language, provide rationale for the criteria. For example, if excluding non-English speaking participants, provide rationale for why it is not possible to include non-English speaking participants.*

**7.3 Vulnerable Populations:** *Check any vulnerable populations that are being targeted for enrollment into the study: (Members of the following populations may not be included as participants in the research unless selected here.)*

 Children/Minors (under 7 years of age)	 Non-Viable Neonates (infants less than 30 days old)
 Children/Minors (7-17 years of age)	 Wards of the State
 Neonates (infants less than 30 days old)	 Fetuses
 Neonates of Uncertain Viability (infants less than 30 days old)	 Pregnant Women

## SHORT TITLE: Lactation at Work

 Adults with impaired decision-making capacity	 CM Employees
	 CM Students/Residents/ Fellows
	 Economically or Educationally Disadvantaged Persons
	 Prisoners

- *For each population selected above, describe the additional safeguards designed to protect their rights and welfare. To ensure that sufficient detail is provided, see the “Tips and Tools for Vulnerable Populations” below for more detailed information on the appropriate protections for each specific population.*
- *If the research involves enrolling CM employees or students, indicate how the potential for employees/students to feel coerced or unduly influenced to participate will be minimized. For example, the risk of coercion may be minimized by ensuring that employees will not be recruited or enrolled by their direct supervisor.*

This protocol is specifically designed for individuals to use a device already in the market designed for lactation (post pregnancy). There could be circumstances where a user becomes pregnant while also providing milk for an existing child, which is also a norm in this population. The risk of coercion for residents and fellows will be minimized by ensuring that employees will not be recruited or enrolled by their direct supervisor.

We will collect the baby's Date of Birth making them a secondary participant. No other information about the baby will be collected. The DIB is collected in order to start the monthly lactation emails. Questions during the survey are targeting the mother's experiences with lactation. Mother's will be asked how old their child is in each monthly survey in order to verify the number month survey and month of pumping are lining up correctly.

## 8.0 Local Number of Participants

**8.1** *Indicate the total number of participants or charts to be enrolled locally as well as the accrual goal. If the study includes multiple groups or cohorts, be sure to describe the number of participants required for each*

## SHORT TITLE: Lactation at Work

*cohort. If one of the groups includes a chart review, each chart is considered a participant and needs to be reflected in the numbers below.*

	Group 1	Group 2 (if applicable)	Totals
Enrollment Goal: Number of participants to be enrolled = the number of participants to be consented or to be screened for chart reviews.  The current rate of pregnancies in training at CMKC is approximately 20-25 per year, with the expansion of this offering we are anticipating that it will at most double. Willow has not indicated a limit on number of devices they will provide.	25 per year		25 per year

## 9.0 Identification and Recruitment of Potential Participants\*

### 9.1 Identification of Potential Participants:

How will participants be identified? (Check all that apply)

- Chart reviews
- By their treating physician who will then provide the study team's contact information to the potential participant/family
- By their treating physician who will obtain patient/family permission to share contact information with the study team
- Self-refer in response to IRB approved advertisements or websites
- Through Cerner or other CM sources (e.g. databases, billing records, pathology reports, admission logs, etc.) May involve access of records by individuals not involved in the patient's care.
- List of candidates provided through the Data Report Request Form
- Registry of individuals interested in research opportunities

- Past participant list
- Participants will roll-over from another research study: Study #
- Other: Six month email notifications to potential subject group in Graduate Medical Education*
- Newsletters and Calendars*

**9.2 Pre-Screening prior to HIPAA Authorization**

Will any of the identification methods checked above involve access to Protected Health Information (PHI) prior to obtaining HIPAA Authorization?

Yes

No

- *If yes, a "Partial Waiver of HIPAA Authorization" is required. Be sure to make this selection in the "HIPAA & Confidentiality" section below and complete [Addendum E: Waiver/Alteration of HIPAA Authorization](#)*

